#### **12.4.2 Analysis of Secondary Endpoints**

Quantification of subjects in each arm achieving PASI50 at week 16, defined as achieving  $\geq 50\%$  reduction in PASI scores measured at week 16 post treatment from baseline, will be summarized. Summary statistics including count and proportion in each treatment arm will be provided for patients enrolled in each arm. Differences in proportions between treatment arms will be summarized along with 95% confidence interval. Exploratory comparison will be carried out using Fisher's exact test.

For change in IGA scores at week 16 post treatment from baseline, summary statistics in terms mean, standard deviation, median and range or inter-quartile range will be generated for each study arm. Between treatment arm differences will be evaluated using a two-sample t-test or the non-parametric Wilcoxon rank sum test where appropriate.

For change in DQLI scores at week 16 post treatment from baseline, summary statistics in terms mean, standard deviation, median and range or inter-quartile range will be generated

for each study arm. Between treatment arm differences will be evaluated using a two-sample t-test or the non-parametric Wilcoxon rank sum test where appropriate.

For change in Itch Scores at week 16 post treatment from baseline, summary statistics in terms mean, standard deviation, median and range or inter-quartile range will be generated for each study arm. Between treatment arm differences will be evaluated using a two-sample t-test or the non-parametric Wilcoxon rank sum test where appropriate.

For longitudinal measurements of the study endpoints obtained overtime, patterns of differences between treatment arms will be evaluated using linear mixed-effects or generalized linear-mixed effects models.

For all these study endpoints, the primary analysis will be carried out on an intention-to-treat basis. For endpoints concerning change at week 16 from baseline, a conservative method for imputation such as last-value carried forward will be used for those missing measurements at week 16. For analysis concerning longitudinal data, no missing imputation will be applied. Secondary per protocol analyses will also be carried out among patients who complied to study treatments.

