## 1. Protocol Summary

|                                |  |
|--------------------------------|--|
| Full Title:             | A Pilot Study of Rimegepant in Moderate Plaque-type Psoriasis  |
| Short Title:            | Rimegepant for psoriasis   |
| Clinical Phase:         | 2  |
| Principal Investigator: | [name]   |
| Study Description:      | 
This proposal is for a double-blind, placebo-controlled pilot study examining the use of an orally administered small molecule competitive inhibitor of the calcitonin gene-related peptide (CGRP) receptor for the treatment of moderately severe plaque-type psoriasis. We hypothesize that interruption of CGRP signaling will prove beneficial in psoriasis.
  |
| Sample Size:            | N=15 for each of 2 cohorts.  |
| Enrollment:             | The study will enroll 30 subjects and we anticipate screening up to 110 subjects.  |
| Study Population:       | Thirty adults with mild to moderate plaque-type psoriasis who are otherwise generally healthy. Subjects for the study will be 18 to 75 years of age.   |
| Enrollment Period:      | The enrollment period will be approximately 3 years 1 month.   |

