#### **12.2 Sample Size/Accrual Rate**

The primary objective of the study is to examine if patients receive the rimegepant treatment had greater improvement in psoriasis in terms of the primary endpoints compared to patients received the placebo. The primary endpoints include both the percent reduction in PASI score post-treatment from baseline and the change IGA score post-treatment from baseline.

The sample size is determined to ensure adequate power to detect clinically meaningful differences in the co-primary endpoints between the treatment arms. With a sample size of 30 patients (15 per treatment arm), we will have 80% power to detect an effect size as small

as 1.06 using a two-sample t-test at a two-sided significance level of 0.05 for each of the primary endpoint. This level of effect size corresponds to >21% differences in the percent reduction in PASI scores post treatment from baseline between the two treatment arms assuming the standard deviation of the percent reduction in PASI score is about 20% which is likely to be a conservative estimate based on published results from trials in patients with moderate to severe disease. This level of effect size also corresponds to a difference of 0.5 in the change of IGA scores between the two study arms assuming the standard deviation of change is around 0.5. Accounting for a dropout rate of 25% a total of 45 patients will be recruited.

The study expects to accrue 5 patients per month and accrue all study patients within 6-10 months.

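### PASI50 is compared with Fisher's exact test, which is valid but well below its 5% level at about 15 per arm; Boschloo's exact test would keep the 5% limit and never lose power, with a gain that depends on the split and the response rates

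*Combined protocol and SAP*

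**What the plan says.** PASI50 at week 16 heads the list of secondary endpoints in the Protocol Summary and in section 12.1. Section 12.4.2 summarises counts and proportions by arm and then states: "Differences in proportions between treatment arms will be summarized along with 95% confidence interval". It does not name the interval method. The test follows: "Exploratory comparison will be carried out using Fisher", with the sentence going on to name the exact test. Section 12.4.1 sets the significance threshold at 0.05.

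On size, the Protocol Summary gives "N=15 for each of 2 cohorts" and section 12.2 bases its power statement on the same number. Section 12.2 then adds: "Accounting for a dropout rate of 25% a total of 45 patients will be recruited". Section 12.3 describes 1:1 permuted-block randomisation with varying block size within two PASI strata. The documents state no PASI50 response rate, and no power or level for this comparison.

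**The concern.** With two small arms, Fisher's test can produce only a limited set of p-values, so its true type I error may lie far below 5%. The unused part of the 5% is lost power, in a trial that has little to spare. An exact unconditional test gives the same 5% guarantee and recovers some of that power.

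A related difficulty is that most intervals for a difference in proportions do not correspond to Fisher's test. The interval can exclude zero while the p-value exceeds 0.05, and one comparison is then reported with two readings. As the interval method is not named, it could also be chosen after the data are seen.

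**Working it through.** **Inputs.** 15 per arm (Protocol Summary; section 12.2); 45 recruited, so about 22:23 (section 12.2); threshold 0.05 (section 12.4.1), taken as two-sided. Response rates are assumptions.

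**The plan's own figure.** Section 12.2 states 80% power for a t-test with effect size 1.06. With 15 per arm the noncentrality is 1.06 × √(15/2) = 2.90 on 28 degrees of freedom, and the power is 80.0%. That figure is reproduced, but it concerns the continuous endpoints. There is no corresponding figure for PASI50.

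**Method.** For arms of n1 and n2, list every table (a, b) and its two-sided Fisher p-value p_F(a, b).

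- Boschloo: p_B(a, b) = maximum over a common rate π of Pr{p_F(A, B) ≤ p_F(a, b)}.
- True level: maximum over π of the binomial probability of all tables with p < 0.05.
- Power: the same sum at two different rates.

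**One table by hand.** For 8/15 v 2/15 (10 responders of 30), the upper tail is [C(15,8)C(15,2) + C(15,9)C(15,1) + C(15,10)C(15,0)] / C(30,10) = (675,675 + 75,075 + 3,003) / 30,045,015 = 0.0251. Doubled, Fisher's p is 0.0502, just above the threshold. The Newcombe 95% interval is 6 to 64 points. Similarly, 9/15 v 3/15 gives Fisher p = 0.060, Boschloo p = 0.030 and Newcombe 5 to 64 points.

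**Level and rejection region.**

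| Split | Fisher, max level | Boschloo, max level | Tables rejected, Fisher / Boschloo |
|---|---|---|---|
| 15:15 | 1.8% | 4.3% | 102 / 122 of 256 |
| 15:14 | 2.8% | 4.4% | 102 / 110 of 240 |
| 14:16 | 3.1% | 4.5% | 112 / 120 of 255 |
| 22:23 | 3.7% | 4.9% | 300 / 308 of 552 |

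In every row, each Fisher rejection is also a Boschloo rejection.

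**Power, Fisher to Boschloo (gain in points).** The first number of each split is placebo, the second rimegepant.

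| Assumed rates | 15:15 | 15:14 | 14:16 | 22:23 |
|---|---|---|---|---|
| 10% v 50% | 53.6 to 67.3 (13.7) | 60.7 to 68.7 (8.0) | 62.6 to 67.9 (5.3) | 82.5 to 85.0 (2.5) |
| 20% v 60% | 44.7 to 59.9 (15.2) | 50.8 to 60.0 (9.2) | 53.5 to 60.8 (7.3) | 75.1 to 79.2 (4.1) |
| 20% v 65% | 56.4 to 71.0 (14.6) | 61.9 to 69.4 (7.5) | 64.0 to 71.4 (7.4) | 85.3 to 87.5 (2.2) |

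At 15:15 the gain falls to 8.0 points at 20% v 40% (11.2% to 19.2%) and 5.6 points at 10% v 70% (89.4% to 95.0%). Swapping which arm is larger changes the unequal-split gains. Over both orientations they run from about 3 to 11 points at 15:14 and 14:16, and stay at about 2 to 4 at 22:23.

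**Test against interval at 15:15.** The Newcombe interval disagrees with Fisher's test on 24 tables and with Boschloo's on 4. At 20% v 60% the chance of disagreement falls from 17.9% to 2.7%. It does not vanish: for 7/15 v 2/15, Boschloo p = 0.055 while Newcombe gives 0.5 to 58 points. Newcombe itself excludes zero up to 5.5% of the time under no effect at 15:15.

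**The case against.** The strongest reply is that nothing here is wrong. Fisher's test never exceeds 5%, section 12.4.2 treats PASI50 mainly descriptively and labels the test exploratory, and no sample size or decision rests on it. That stands: this is a question of efficiency and consistency.

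A second reply is that the 15:15 figures flatter the case. That also stands. Blocking with varying sizes in two strata does not guarantee equal arms, and section 12.2's 45 conflicts with the 30 stated elsewhere. A reader might infer that Fisher's level is at most 1.8% in this trial and that the switch is worth 11 to 15 points generally. The documents support neither: the first fails once the arms differ by one patient, and the second also needs response rates that the documents do not give.

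A reader might also infer that the gain is free. It is free in patients and data, but the power comes from a higher actual type I error, within the nominal limit.

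Third, Boschloo's test needs a definition when arms are unequal. For 10/15 v 4/14, ordering by Fisher's two-sided p-value gives 0.061, while one common software routine gives 0.049. This is a reason to state the definition, not to keep Fisher's test.

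What the objections do not remove is the nesting: at every size checked, Boschloo's test rejected all that Fisher's rejects and stayed below 5%.

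**Conclusion.** The point holds as a cheap improvement. Fisher's test uses 1.8 of the 5 percentage points at exactly 15:15, and 2.8 to 3.7 at the unequal splits tabulated. Boschloo's test uses 4.3 to 4.9 and is never less powerful at the sizes checked. In the three scenarios with differences of 40 to 45 points, the gain is about 14 to 15 points at 15:15. With the arms oriented as in the power table, it is about 5 to 9 points at 15:14 or 14:16, and about 2 to 4 at 22:23. For smaller or very large differences at 15:15 it is about 6 to 8 points.

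These figures rest on assumed response rates, a two-sided 0.05 threshold, Boschloo's test ordered by Fisher's two-sided p-value, and the numbers actually analysed. Neither test uses the PASI strata.

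It would go too far to say that the plan contradicts itself on test and interval. Conflict is possible with common intervals, but the plan names none, so the gap is one of specification.

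**What to change.** In section 12.4.2:

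- Replace Fisher's test with Boschloo's exact unconditional test at two-sided 0.05. State the two-sided definition, for example ordering tables by Fisher's two-sided p-value, so that unequal arms give one answer. Keep the exploratory label.
- Name the interval for the difference in proportions. Preferably obtain it by inverting an exact unconditional test, with the statistic named. A Newcombe interval is an acceptable simpler choice if the SAP acknowledges that it can occasionally disagree with the test and can slightly exceed the nominal error.

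The cost is one or two sentences, with no extra patients, data or visits. The one real downside is the rise in maximum type I error from 1.8% to 4.3% at 15:15, still within 5%. Even if Fisher's test is kept, the interval method should be named before unblinding.

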## **12.5 Interim Analysis**

Not applicable.

## **12.6 Reporting and Exclusions**

### **12.6.1 Evaluation of Toxicity**

All subjects will be evaluable for toxicity from the time of their first treatment with the *Investigational Agent*. Consultation with the Biostatistics Office will allow for completion of this section.

### **12.6.2 Evaluation of Response**

All subjects included in the study will be assessed for response to treatment if they have received at least 4 weeks of treatments.

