### **7.10 Duration of Follow Up**

Subjects will be followed for 4 weeks after discontinuation of the investigative pharmaceutical agent. Subjects removed from study for unacceptable adverse events will be followed until resolution or stabilization of the adverse event.

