### **8. Study Intervention Discontinuation and Participant Discontinuation/Withdrawal**

#### **8.1 Discontinuation of Study Intervention**

Subjects will be withdrawn from study treatment permanently for the following reasons:

1. Development of any hypersensitivity phenomena that may be related to the study medication.
2. Excessive nausea making continuation of participation in the study impossible.
3. Development of any intercurrent illness or medical need to take a medication such that exclusion criteria apply.
4. Occurrence of pregnancy in a female subject.
5. If any clinical adverse event (AE), laboratory abnormality, or other medical condition or situation occurs such that continued participation in the study would not be in the best interest of the participant
6. Disease progression which requires discontinuation of the study intervention
7. If the participant meets an exclusion criterion (either newly developed or not previously recognized) that precludes further study participation

Subjects will be referred for appropriate medical care for any adverse effects.

Subjects will continue to be followed for assessment of disease severity until the 20-week period is over.

Discontinuation of treatment does not mean discontinuation from the study, and remaining study procedures (assessments of disease severity) will be completed as indicated by the study protocol.

If a clinically significant finding is identified (including, but not limited to changes from baseline) after enrollment, the investigator or qualified designee will determine if any change in participant management is needed. Any new clinically relevant finding will be reported as an adverse event (AE).

**Criteria for interrupting the study:** We will have a study monitoring committee (SMC) consisting of the study PI, the medical monitor and 1 investigator not directly involved in the conduct of this study. This committee will review all Grade 3 or 4 events, and all SAEs in real time. We will pause enrollment of new participants if there is 1 or more Serious Adverse Events that are at least possibly related to study drug, or 2 or more Grade 3 or 4 events at least possibly related to study drug. The enrollment of participants will not resume until the SMC reviews the adverse events and agrees unanimously to resume enrollment.

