## 8.2 Participant Discontinuation/Withdrawal from the Study

Participants are free to withdraw from participation in the study at any time upon request. An investigator may discontinue or withdraw a participant from the study for the following reasons:

1. Pregnancy. However, subjects will be followed until the end of the pregnancy.
2. Significant study intervention non-compliance (failure to take medications, refuses to allow study procedures).
3. Participant lost to follow-up after 3 attempts to contact subject to schedule study visit.

The reason for participant discontinuation or withdrawal from the study will be recorded on the Case Report Form (CRF). Subjects who sign the informed consent form and are randomized but do not receive the study intervention may be replaced. Subjects who sign the informed consent form, and are randomized and receive the study intervention, and subsequently withdraw, or are withdrawn or discontinued from the study will not be replaced.

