### **12.4 Analysis of Endpoints**

#### **12.4.1 Analysis of Primary Endpoints**

The primary endpoint is the week 16 PASI score. We will calculate the percent reduction in week 16 PASI scores post treatment from baseline. Summary statistics in terms mean, standard deviation, median and range or inter-quartile range will be generated for each study arm. Between treatment arm differences will be evaluated using a two-sample t-test or the non-parametric Wilcoxon rank sum test where appropriate. The primary analysis will be carried out on an intention-to-treat basis. Last value carried forward will be used to impute for patients missing week 16 measurements. Per-protocol analysis will also be carried out among patients who are deemed compliant to treatment (defined as at least 75% of doses taken as measured by pill counts) and had both baseline and week 16 measurements will also be carried out using similar statistical methods. P-values less than 0.05 will be considered statistical significant.

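### The 4-week treatment condition in 12.6.2, if applied to the efficacy endpoints, is a post-randomisation exclusion that contradicts the intention-to-treat basis in 12.4.1 and 12.4.2

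*Combined protocol and SAP*

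**What the plan says.** Section 12.4.1, on the primary endpoint: "The primary analysis will be carried out on an intention-to-treat basis". On missing data it adds: "Last value carried forward will be used to impute for patients missing week 16 measurements". Section 12.4.2 extends the same basis to the secondary endpoints: "For all these study endpoints, the primary analysis will be carried out on an intention-to-treat basis". Neither section sets a minimum duration of treatment.

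Section 12.6.2, which falls under the heading Reporting and Exclusions, reads: "All subjects included in the study will be assessed for response to treatment if they have received at least 4 weeks of treatments".

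Three other places bear on it:
- The per-protocol set in 12.4.1 depends on compliance, "defined as at least 75% of doses taken as measured by pill counts", and on having both baseline and week 16 measurements.
- Section 8.1, on subjects who stop study drug: "Subjects will continue to be followed for assessment of disease severity until the 20-week period is over". It attaches no 4-week condition.
- Section 7.10 gives a different follow-up period: "Subjects will be followed for 4 weeks after discontinuation of the investigative pharmaceutical agent".

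**The concern.** A randomised subject who stops study drug in week 3 is in the efficacy analysis under 12.4.1 and 12.4.2, but is not assessed for response under 12.6.2. Duration of treatment is determined after randomisation. The reasons for stopping listed in 7.9 and 8.1 include adverse events, nausea, hypersensitivity and disease progression, and these can differ between active drug and placebo. Leaving such subjects out gives up the protection of randomisation, and the direction of the resulting bias cannot be known in advance.

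There is also a question of discipline. If anyone stops before week 4, the text can support two sets of subjects for PASI and PASI50. Section 7.11 leaves the statistician unblinded, so the set should be settled in writing before data are seen.

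**Working it through.** **Is 12.6.2 another name for a set already defined?** Every-other-day dosing for 16 weeks is 16 × 7 / 2 = 56 doses.
- Per-protocol threshold: 0.75 × 56 = 42 doses.
- Four weeks of treatment: 4 × 7 / 2 = 14 doses, and 14/56 = 25%.

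So the 4-week rule is not the per-protocol set. It is not intention-to-treat, which has no exposure threshold. Nor is it a visit-scheduling rule, because 8.1 continues severity assessments to week 20 after drug is stopped.

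**The plan's own figure.** Section 12.2 gives 15 per arm, effect size 1.06, a two-sample t-test, two-sided 0.05 and 80% power. The noncentral t calculation gives 80.0%, so the figure reproduces. With the stated SD of 20 points, the design difference is 1.06 × 20 = 21.2 points.

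**Size of the shift (illustration).** The documents give no early-stop rate and no outcome for early stoppers. Assume a net one subject is excluded from one arm, and that this subject's PASI reduction is g points below the mean of those retained in the arm. Then:

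shift = g / n; SE = 20 × √(2/n)

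| n per arm | SE | g = 10 | g = 21.2 | g = 30 |
|---|---|---|---|---|
| 15 | 7.30 | 0.67 points (0.09 SE) | 1.41 (0.19 SE) | 2.00 (0.27 SE) |
| 22.5 | 5.96 | 0.44 points (0.07 SE) | 0.94 (0.16 SE) | 1.33 (0.22 SE) |

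The second row is there because 12.2 recruits 45, while the Protocol Summary enrols 30. With no true effect and 15 per arm (28 df, noncentrality = shift / 7.30), the two-sided 5% error rate becomes 5.1%, 5.4% and 5.8%. The sign of the shift depends on which arm loses the subject.

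**Is an affected subject plausible?** If the 25% dropout in 12.2 occurred at a constant rate over 16 weeks (an assumption), the share stopping before week 4 would be 1 − 0.75^(4/16) = 6.9%, about 2 of 30 across both arms.

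**Cost of keeping early stoppers.** Suppose one subject per arm is kept at zero change and the other 14 have mean reductions m (placebo) and m + 21.2 (active). The expected difference is (m + 21.2) × 14/15 − m × 14/15 = 21.2 × 14/15 = 19.8 points, whatever m is. Power does depend on m, because a zero sitting far from the arm mean adds variance. By simulation (SD 20, 15 per arm), power is about 76%, 75% and 72% at an assumed placebo mean reduction of 0, 10 and 20 points. If that subject is excluded from each arm (14 and 14), power is 77%.

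**The case against.** The strongest reply is that 12.6.2 does not say what it is being charged with. It names no endpoint, analysis set or test, and it does not say that anyone is removed from a comparison. Response is not defined anywhere, since 10.1 Response Criteria is marked not applicable. Section 12.6.1 beside it is visibly unfinished, which suggests template text. Sections 12.4.1 and 12.4.2 are specific, and would ordinarily prevail. Investigators also stay blinded until the analyses are complete (7.11).

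Much of this stands. A reader might infer that the plan sets up a third efficacy population, or that its primary analysis is not really intention-to-treat. The documents do not support that: it is the natural reading of 12.6.2 if someone applies it to PASI or PASI50, not something the text states.

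A reader might also infer that the 4-week condition costs power. That does not follow either. Whether exclusion lowers or raises power depends on how early stoppers would otherwise be handled, and in the zero-change case above exclusion gives the higher power. The case against exclusion is bias and ambiguity, not power.

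Finally, similar losses with similar gaps in both arms would largely cancel, so the shifts shown need an imbalance.

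What survives is that the sentence is current text under a heading about exclusions, nothing labels it as supplementary, and nothing reconciles it with intention-to-treat.

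**Conclusion.** The point holds as a conflict in wording that should be fixed. If 12.6.2 is followed for the PASI or PASI50 analyses, it is a post-randomisation exclusion and contradicts the stated intention-to-treat basis. The contradiction rests on the text alone.

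Its size rests on assumptions that the documents do not supply: an imbalance of one early stopper between arms and a gap of 10 to 30 points. On those assumptions the effect is small, at most 0.27 of a standard error with 15 per arm. It would grow with a larger imbalance, but nothing in the documents points to one.

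**What to change.** Replace 12.6.2 with: *All randomised subjects are included in the response analyses in the arm to which they were randomised, regardless of treatment duration.* If a 4-week set is wanted, define it there as a labelled sensitivity analysis.

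As a consequence, add to 12.4.1 and 12.4.2 that when a subject has no post-baseline value, the baseline value is the last value carried forward (zero change). The present rule can be read that way, since PASI is scored on Day 0, but it does not say so.

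Two related matters are separate from this defect:
- Sections 7.10 and 8.1 should be reconciled. Read literally, under 7.10 a subject who stops before week 4 is last seen before week 8 (4 + 4), so the week 16 value is imputed; under 8.1 it is observed.
- Section 8.2 says: "Subjects who sign the informed consent form and are randomized but do not receive the study intervention may be replaced". The plan should state how such replaced subjects are counted.

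The cost is a few sentences. The statistical price is some dilution: with one zero-change subject per arm, the design difference falls from 21.2 to 19.8 points and power is about 72% to 76%, against 77% under exclusion. That is the usual price of an intention-to-treat comparison and should be accepted knowingly.
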